Many hematologic malignancies are diseases of aging.^{1,2} For example, the median age at time of diagnosis for patients with acute myeloid leukemia (AML), non-Hodgkin lymphomas (NHL), and multiple myeloma (MM) are 68, 67, and 69 years, respectively.¹ Recently, there have been advances in treatment options for older adults with hematologic malignancies. For example, in the last decade, lower-intensity outpatient treatments with reduced treatment-related mortality rates and potentially similar efficacy to standard first-line intensive inpatient chemotherapy have become available to patients with AML.⁴⁻⁶ Despite hematologic malignancies being more common in older populations and recent treatment advances, survival rates for older adults with hematologic malignancies remain poorer than their younger counterparts.¹ In older patients with AML, for example, the median overall survival rates range from 6-12 months. In addition, hospitalizations due to treatment- and disease- related adverse events are common.

1.2. Patients with hematologic malignancies receive more aggressive care at the end-of-life (EOL) compared to those with solid tumors.

Previous studies have established quality indicators to guide optimal care at the EOL.^{8,9} These quality indicators include healthcare utilization [emergency department (ED) visits, hospitalizations, intensive care unit (ICU) admission, life-sustaining treatments (LSTs), chemotherapy administration, and receipt of transfusion] at EOL, completion of Medical or Physician Orders for Life Sustaining Treatment (MOLST/POLST) forms, utilization of palliative care and hospice services, and place of death. Compared to patients with solid tumors, patients with hematologic malignancies are more likely to visit the ED, be hospitalized, be admitted to ICU, and to receive LSTs, transfusions, and chemotherapy at the EOL.^{3,10,11} They are also less likely to complete MOLST/POLST forms in a timely fashion, less likely to receive palliative care and hospice services, and more likely to die in the hospital.^{3,10} Therefore, interventions are needed to improve EOL care in patients with hematologic malignancies.

1.3. Advance care planning (ACP) may improve EOL care for older patients with hematologic malignancies.

ACP is a process that supports adults in understanding and sharing their personal values, life goals, and preferences regarding medical care. These decisions can then be recorded in MOLST/POLST forms to guide surrogate decisions makers if the patient loses decision making capacity. Our preliminary data demonstrates that among adults with AML and myelodysplastic syndrome (MDS) seen at the Wilmot Cancer Institute (WCI) and its affiliated community centers, most MOLST forms were completed late in the disease course.¹² Compared to patients who completed MOLST \leq 30 days prior to death or never completed MOLST, those who

completed MOLST >30 days prior to death were less likely receive inpatient care and more likely to utilize hospice at the EOL, indicating early MOLST completion is associated with better EOL care. Interventions to improve access to ACP and MOLST/POLST completion can therefore be expected to improve EOL care.

1.4. Evidence-based interventions can improve access to ACP but are not tailored to older adults with hematologic malignancies.

The Serious Illness Care Program (SICP) is an evidence-based intervention to enhance EOL conversations between physicians and patients with advanced cancer in the outpatient setting.¹³ It consists of the Serious Illness Conversation Guide (SICG) as well as training and system-level support for physicians to conduct conversations about ACP. In a phase III randomized trial, compared to the control arm, more patients and physicians in the intervention arm had serious illness conversations (96% vs. 79%) and these conversations occurred 2.4 months earlier and were more comprehensive and patient centered. However, less than 10% had hematologic malignancies. Therefore, we have adapted the SICP for older patients with hematologic malignancies based on feedback from clinicians [oncologists, palliative care physicians, advanced practice providers (APP), and nurses)], older patients with these diseases, and their caregivers.

1.5. Previous research has shown that advanced practice providers-initiated ACP discussions improve ACP engagement.

APPs play an important role in the care of patients, especially in the inpatient setting at the Wilmot Cancer Institute, alongside the attending physician and hematology/oncology trainee physician. APP-initiated ACP discussions have been shown to improve patient understanding of ACP and completion of advance directives for patients with cancer.¹⁴ Furthermore, implementation of APP roles in inpatient settings, including critical care, have been shown to improve patient satisfaction and cost of care.¹⁵ Therefore, an inpatient APP-delivered ACP intervention for patients with hematologic malignancies may improve care for this patient population.

1.6. Overall goal

The long-term goal of this proposal is to improve ACP access and EOL care in older patients with hematologic malignancies via an inpatient ACP intervention delivered by APPs and hematology/oncology trainee physicians (hereby referred to as fellows).

The objective of this two-year project is to create training materials and processes for an inpatient ACP intervention and to assess its preliminary efficacy in older patients with hematologic malignancies in a single arm study (comparing data to historical control).¹³

2.0. Aim and Hypothesis

2.1 Primary Aim

To adapt training materials and processes for an inpatient ACP intervention delivered by APPs and hematology/oncology fellows (completed).

2.2. Secondary Aim

To assess the feasibility of an inpatient ACP intervention, as well as the preliminary efficacy of the intervention on completion of advance directives (e.g., MOLST form, healthcare proxy form) and on EOL care (e.g., intensive care unit admissions, life-sustaining treatments, readmission rates, hospice enrollment, inpatient death).

2.3. Hypothesis

An inpatient ACP intervention delivered by APPs and hematology/oncology fellows will improve completion of advance directives and EOL care.

3.0. Study Design and Population

3.1. Study Setting

Wilmot Cancer Institute (WCI), University of Rochester Medical Center (URMC)

3.2. Study Type

Aim 1: Qualitative study (phase 1) - completed

Aim 2: Single-arm pilot study (phase 2)

3.3. Study Population

Aim 1 (completed): We will discuss the study at APP meetings and solicit interest in participation. [name] will serve as the APP lead and has preliminarily solicited support from APPs on the inpatient hematology service. We will approach APPs in person or via email communications. We will conduct focus group interviews to obtain feedback on training materials (e.g., prerecorded vs. interactive sessions, duration of training) and processes (e.g., workflow, template to document ACP visit in the electronic medical record) in the inpatient setting. Interviews will be audio-recorded by study personnel and then transcribed. Two trained personnel (“coders”) will extract and highlight themes from the transcripts. We anticipate up to 15 APPs will participate in this aim.

Version Date: 5/10/23

PRMC#: UOCPC22039

Study Protocol

ClickIRB #: STUDY00007403

Results from Aim 1 will be used to adapt the inpatient APP-delivered ACP intervention for use in Aim 2 (these will be shared with APPs via email prior to Aim 2 so they can review how their feedback was used to adapt the intervention). In other words, Aim 2 will occur after Aim 1 has been completed.

Aim 2: We will conduct a single arm study of 50 older patients, their caregivers (up to 2 caregivers per patient), and APPs/hematology/oncology fellows. We will approach all APPs on the inpatient hematologic malignancy service for Aim 2, with a goal of between 10-15 APPs participating. We will discuss the study at hematology/oncology fellow meetings and PIs ([name] [name] and [name]) will lead efforts to solicit support and involvement from fellows. We will approach all hematology/oncology fellows at Wilmot Cancer Institute for Aim 2, with a goal of between 10-12 fellows participating. We will consent up to 252 participants (75 patients, 150 caregivers, 15 APPs, 12 fellows) to account for screen fail or withdrawal with the target number being 50 patients and 100 caregivers.

3.4. Inclusion and Exclusion Criteria for Clinicians (Aim 1 and Aim 2)

Inclusion criteria:

Aim 1 (completed)

- APP on the inpatient malignant hematology service [including both physician assistants (PA) and nurse practitioners (NP)]

Aim 2

- APP on the inpatient malignant hematology service [including both physician assistants (PA) and nurse practitioners (NP)]
- Hematology/Oncology fellows at the Wilmot Cancer Institute

Exclusion criteria

- None

3.5 Inclusion and Exclusion Criteria for Patients (Aim 2)

Inclusion criteria:

- Age \geq 60 years
- A diagnosis of hematologic malignancy [including but not limited to acute leukemia, myeloid malignancies (e.g., atypical CML, MDS/MPN overlap syndromes, CMML), multiple myeloma, lymphoma, or any other hematologic malignancies based on the primary oncologist's judgment]
- Able to provide informed consent
- Being managed in the inpatient setting
- English-speaking

Version Date: 5/10/23

PRMC#: UOCPC22039

Study Protocol

ClickIRB #: STUDY00007403

Exclusion criteria

- None

3.6 Inclusion and Exclusion Criteria for Caregivers (Aim 2)

Inclusion criteria:

- Age \geq 18 years
- Selected by patient when asked if there is a “*family member, partner, friend, or caregiver with whom you discuss or who can be helpful in health-related matters*”
- Able to provide informed consent
- English-speaking

Exclusion criteria

- None

3.7. Number of Subjects

Aim 1: We plan to enroll APPs on the inpatient malignant hematology service. This phase will consist of focus group interviews with APPs. We plan to enroll up to 15 APPs. We will conduct at least two and up to four focus groups. We anticipate thematic saturation will be reached with this number of participants based on previous studies (i.e., the point at which no new data emerge).^{17,18}

Aim 2: We plan to enroll 50 patients total and their caregivers (up to 2 caregivers per patient if available) in 18 months. On average, 2-4 patients with hematologic malignancies are admitted to Wilmot Cancer Institute every day (and on average, the inpatient malignant hematology service cares for 15-25 patients daily). Our team has a proven track record in recruiting older patients with hematologic malignancies to supportive care and quality improvement studies (65-75% consent rate).^{17,18} Therefore, recruiting 50 patients and their caregivers [approximately 150 participants (50 patients; 100 caregivers), but can consent up to 225 patients/caregivers to account for screen fail/withdrawal; 75 patients and 150 caregivers] over 18 months is feasible. Patients and caregivers participation in this study will last approximately 4 weeks.

APPs who consent to the study in Aim 1 will also be consented to participate in Aim 2. APPs can also consent and join the study in Aim 2, after Aim 1 has been completed. Therefore, participation in Aim 1 of this study will last for 1 day for APPs and participation in Aim 2 of the study will last approximately 18 months for APPs. We plan to consent hematology/oncology fellows to participate in this study for Aim 2 only, since Aim 1 of this study has already been completed. Therefore, fellows will not participate in the focus group interviews. Participation in this study will last approximately 18 months for hematology/oncology fellows participating in Aim 2.

Version Date: 5/10/23

PRMC#: UOCPC22039

Study Protocol

ClickIRB #: STUDY00007403

3.8. Gender of Subjects

The gender ratio of enrolled patients will be similar to the gender ratio of each hematologic malignancy in older adults (e.g., approximately 1.2:1 to 1.5:1 male to female ratio for AML patients).^{19,20}

3.9. Age of Subjects

We will recruit patients with hematologic malignancies aged 60 and above (from date of consent, confirmed on electronic medical record).

3.10. Racial and Ethnic Origin

In Rochester, New York, Whites, African Americans, and Hispanics make up approximately 65%, 30%, and 5% of the population (Race and Ethnicity in Rochester, NY statistical atlas). We expect participants to be similar to these statistics. Certain hematologic malignancies are more common in Caucasian individuals, including leukemia and lymphoma, while hematologic malignancies such as multiple myeloma are more common in African American individuals. We expect our participants will be similar to this epidemiology. As enrollment is limited to English-speaking patients, we predict a higher percentage of Caucasian individuals. The study does not restrict enrollment based on race or ethnicity. Because our intervention materials are written in English, we will only enroll English-speaking patients.

3.11. Vulnerable Subjects

Recruitment will exclude vulnerable populations such as fetuses, neonates, children, pregnant women, prisoners, and institutionalized individuals. We will also exclude adults who are deemed to not have decisional capacity and those who lost their consent capacity during the study period, as per their treating oncologist.

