7.2.3.11. Feasibility metrics

Feasibility metrics will be collected:

- Retention rate (percentage of patients consented to the study ultimately completing all study components) – primary metric
- Recruitment rate (percentage of patients who are approached and agree to enroll) will also be described.

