Qualitative analyses: We anticipate thematic saturation will be reached with this number (N=approximately 10-15) of participants based on previous studies (i.e., the point at which no new data emerge).^{16,17} All interviews will be conducted and audio-recorded by study personnel and then transcribed by a professional transcription service. Two trained personnel (“coders”) will extract and highlight themes from the transcripts. We will analyze the qualitative data using grounded theory and constant comparative methods, with coding to structure data into categories and create groups according to the broader issues or themes.³¹ The themes will focus on feedback on training materials (e.g., prerecorded vs. interactive sessions, duration of training) and processes (e.g., workflow, template to document ACP visit in the electronic medical record) in the inpatient setting. These interviews will be audio-recorded by study personnel and then transcribed. We will keep an audit trail to establish trustworthiness. We will critically examine the data collection and analysis process, discuss emerging codes, and reach consensus on principal themes. These themes will be used to adapt the inpatient APP/fellow-delivered ACP intervention.

[figure not shown]
8.2.2 Analysis Plan for Aim 2

Quantitative analyses: We will use descriptive statistics to summarize feasibility metrics and all measures. Feasibility will be defined based on the retention rate (% of patients approached who consented and complete the ACP visit); >70% will be considered a successful benchmark for feasibility. Rates will be presented with associated two-sided 95% exact binomial confidence

intervals. A sample size of 50 patients produces a confidence interval with a maximum width of 0.29 (limits 0.36-0.65), when the observed feasibility rate is 0.50. We anticipate a higher feasibility rate, which will result in a narrower confidence interval. If the observed feasibility rate is 0.70, the width of the confidence interval is reduced to 0.24 (limits 0.55-0.82). If more than 50 patients are approached, then the confidence intervals will become narrower. Recruitment rate will be the % of patients approached who agree to participate (i.e., consent), and will be described similarly.

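### The primary feasibility metric, the retention rate, is defined in two incompatible ways (sections 7.2.3.11 and 8.2.2), and the only >70% benchmark is attached to one of them

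*Combined protocol and SAP*

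**What the plan says.** Section 7.2.3.11 labels retention the primary feasibility metric and defines it as the "percentage of patients consented to the study ultimately completing all study components". It gives no threshold and does not list the components.

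Section 8.2.2 says feasibility rests on the retention rate, defined there as the percentage "of patients approached who consented and complete the ACP visit); >70% will be considered a successful benchmark for feasibility". It promises exact 95% binomial intervals, works them for 50 patients, and adds: "If more than 50 patients are approached, then the confidence intervals will become narrower". It then defines a separate metric: "Recruitment rate will be the % of patients approached who agree to participate (i.e., consent), and will be described similarly".

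Section 3.7 sets the target at 50 enrolled patients, allows up to 75 to be consented, and cites earlier recruitment to "supportive care and quality improvement studies (65-75% consent rate"). Sections 4.3 and 7.1 place post-intervention measures after the ACP visit and an interview within four weeks of it.

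On capacity, section 3.5 requires patients to be "Able to provide informed consent". Section 3.11 states: "We will also exclude adults who are deemed to not have decisional capacity and those who lost their consent capacity during the study period". Section 3.7 says "Patients and caregivers participation in this study will last approximately 4 weeks", while section 7.1 plans chart follow-up lasting up to five years or to death. Section 4.2 lets study personnel withdraw a participant but does not mention loss of capacity.

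**The concern.** Retention is the only metric with a success criterion, so the pilot's feasibility conclusion depends on it. The primary-metric label sits beside one definition and the benchmark beside the other, and nothing says which governs. The same data could be reported as feasible or not feasible, and the choice could be made after the results are known.

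If the denominator in 8.2.2 is patients approached, every refusal counts against retention. Retention then cannot exceed the recruitment rate, which the plan already reports on its own.

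Section 3.11 bears on this at one place. A patient who has the ACP visit and then loses capacity before the interview is a completer under 8.2.2 and a non-completer under 7.2.3.11. How that patient should count is not stated.

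**Working it through.** **The plan's own intervals (8.2.2, Clopper-Pearson, n = 50).**
- 25/50: 0.355 to 0.645, width 0.2895. The stated width of 0.29 reproduces; the stated upper limit of 0.65 should round to 0.64.
- 35/50: 0.554 to 0.821, width 0.267. The stated limits (0.55-0.82) reproduce, but the stated width of 0.24 does not: 0.82 - 0.55 = 0.27. This is a separate slip, and nothing below depends on it.

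**Inputs.** 50 consented, the 65-75% consent rate (both section 3.7) and the >70% benchmark (8.2.2). The counts 33, 36 and 45 are hypothetical; the documents give no expected counts.

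**Numerator conflict alone, consented patients as denominator.** Suppose 36 of 50 have the visit and 33 complete everything.
- ACP visit: 36/50 = 72.0% (95% CI 57.5-83.8%), benchmark met.
- All components: 33/50 = 66.0% (51.2-78.8%), not met if the 8.2.2 benchmark is carried over to 7.2.3.11, which states none.

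**Denominator conflict, approached patients as denominator.** Approached = consented / consent rate: 50/0.75 = 66.7, so 67; 50/0.65 = 76.9, so 77. The rate is the consent rate multiplied by completion among consented, so the effect does not depend on exactly 50 being consented.
- 36 visits: 36/67 = 53.7% and 36/77 = 46.8%, against 72.0% of consented.
- 45 visits: 45/50 = 90.0% of consented (78.2-96.7%), but 45/67 = 67.2% (54.6-78.2%) and 45/77 = 58.4% (46.6-69.6%) of approached.
- Ceiling, all 50 complete: 50/67 = 74.6% and 50/77 = 64.9%.
- Needed at 75% consent: completion above 0.70/0.75 = 93.3%. 46/67 = 68.7% fails and 47/67 = 70.1% passes, so at least 47 of 50.
- At 70% consent the rate is at most 0.70 x 1 = 70%, which does not exceed 70%. At 65% the benchmark is out of reach.

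**Which denominator 8.2.2 means.** Its wording can be parsed either way. The sentence "If more than 50 patients are approached, then the confidence intervals will become narrower" ties precision to the number approached, which favours approached patients. Against that, the intervals are worked at n = 50, which is the enrolment target.

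**The case against.** The strongest reply is that the sponsor probably meant consented patients throughout. The intervals use the enrolment target, recruitment is reported separately, and a definition that makes its own benchmark nearly unattainable is unlikely to be intended. This has force, and it limits the size: the large discrepancies and the unreachable benchmark hold only with approached patients as denominator. With consented patients, only the numerator conflict remains, and it matters near 70%. But the interval sentence points the other way, and the numerators differ on either parse.

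A second reply is that 8.2.2 controls, since it alone carries the benchmark. That is tenable, but 7.2.3.11 still names a different quantity as primary. A third is that this is a descriptive pilot with no test attached to 70%. That is true, yet this is the only success criterion it has.

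A reader might infer more from section 3.11: that patients who lose capacity are dropped from the analysis, which would inflate retention or distort the end-of-life indicators. The documents do not support this. The paragraph opens by speaking of recruitment, and the clause could cover loss of capacity between approach and signature. That 3.5 already requires ability to consent shows little about intent, because 3.11 is largely redundant anyway. No section removes these patients, and 7.1 and 7.2.3.11 read literally keep them in. A shift such as 35/50 = 70.0% to 35/49 = 71.4% would arise only if a non-completer were dropped, and it sits exactly on a strict cutoff. What remains is an ambiguity: the clause can also naturally be read as reaching enrolled patients, and its study period is not defined. The consent form, which may settle part of this, was not available for review.

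**Conclusion.** The definition conflict stands on the text. The numerators of the primary feasibility metric are incompatible on any reading, and on the natural reading of 8.2.2 the denominators are as well.

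The size depends on the denominator. With consented patients, the verdict can differ when results fall near the threshold (72.0% against 66.0% in the example). With approached patients, at the protocol's own consent rates, it can differ well away from it: 90.0% of consented becomes 58.4-67.2% of approached, and the most that can be achieved is 64.9-74.6%. These figures rest on hypothetical counts and on the 65-75% consent rate holding in this study; the conflict itself rests on neither.

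Section 3.11 is a secondary clarification. No rate of capacity loss is given or assumed, and no effect on the end-of-life results is claimed. This should be corrected before the feasibility result is analysed.

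**What to change.** Put one retention definition in both 7.2.3.11 and 8.2.2. All consented patients are the preferable denominator, because consented over approached is already reported as recruitment; the documents require reconciliation rather than this particular choice. Name the components that must be completed for the numerator. Apply >70% and the confidence-interval statements to that definition only, and reword the sentence about patients approached to match.

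Keep the protection in 3.11 and add a sentence or two reconciling it with 4.2, 7.1 and the retention definition. State that an enrolled patient who later loses capacity stays in the retention denominator, and whether chart follow-up continues as far as the consent form allows.

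The cost is a short text amendment and a check of the consent form. No new visits or data are needed: the approached, consented and completed counts are already required by the planned metrics, and chart follow-up is already planned.
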